Inclusion/ Exclusion Criteria	
 
Exclusion Criteria:
 
Pregnancy (all women of child-bearing age would be questioned and told by the consenting physician regarding that criteria).
 
All current practice PEG contraindication
 
Acute gastrointestinal bleeding
 
Extreme obesity patients (BMI>40)
 
Emergency endoscopy
 
Infectious disease local or systemic (e.g sepsis, pancreatitis)
 
Known esophageal pathology (e.g stenosis, eosinophilic esophagitis, varices, achalasia, reflux)
 
In case of PEG replacement: lack of a well healed gastrostomy or Infection around the insertion site.
 
Known gastric pathology that may prevent safe device insertion, feeding, removal and Bumper flanges expulsion according to the investigator discretion.
 
Any history of bowel obstruction, pseudo-obstruction.
 
Crohn's disease
 

fic	edical M	– Study Protocol –	Protocol No.: FM-01 Version 5.1 Page 10 of 55	
Safety and Usability Evaluation of the Fidmi Low-Profile Enteral Feeding Device		CONFIDENTIAL		
	
 
12. Severe GERD, recurrent vomiting
 
13. Inability to tolerate sedated upper endoscopy due to cardic pulmonary instability or other contraindication to endoscopy
 
14. Current enrollment in an investigational drug or device study o participation in such a study within 30 days of entry into this study
 
			copy e study or
Study Duration	Per Patient: between 120 days±14 days, depending on the interval between pre-operative visit (inclusion) and day of operation. Total 8 months to recruit and treat 15 patients.			
Statistical Analysis Plan	NA. Feasibility safety study. Descriptive statistics will be provided.			

ficmedical	– Study Protocol –	Protocol No.: FM-01 Version 5.1 Page 11 of 55
Safety and Usability Evaluation Enteral Feeding Device	CONFIDENTIAL	

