#### **Bumper flanges expulsion**

18. Sensation in communicating patients.

fic medical	– Study Protocol –	Protocol No.: FM-01 Version 5.1 Page 25 of 55
Safety and Usability Evaluation Enteral Feeding Device	of the Fidmi Low-Profile	CONFIDENTIAL

19. Complete expulsion fluoroscopically proven by abdominal X-Ray imaging (in case particle/s from the bumper can be seen in the imaging a further follow visit will be scheduled only in case of symptoms related event/s, as per physician discretion)

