#### Study PEG removal Form:

Procedure duration, heart rate at the end of the operation, amount and type of analgesia consumed, postoperative bleeding, use of anti-bleeding agents (such as tranexemic acid (hexakapron)).

Endoscopist feedback Form: Endoscopist 10-point Visual Analogue Scale for removal procedure difficulty.

- d) Patient PEG removal/ replacement Feedback Form
- e) Study Patient Discharge form.

The discharging study investigator will instruct the patient (or his care giver) to immediately call the site in case of: vomiting, swollen belly, repeated abdominal aches and general deterioration (for demented patients). In case there is a suspicious of GI perforation or hemorrhage bowel obstruction the study investigator will schedule an un-scheduled visit.

C medical	– Study Protocol –	Protocol No.: FM-01 Version 5.1
		Page 37 of 55
Safety and Usability Evaluation of the Fidmi Low-Profile		CONFIDENTIAL
Enteral Feeding Device		

The patient will be asked for his most convenient day for the termination visit (Visit 7 study termination, see below) - this day will be recorded by the study nurse at the Patient Visits Log.

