## Visit 7: Follow up after 4 months +/- 10, X-ray and termination visit

In compliance with the Centric Patient Approach, a home X-ray examination will be offered to the patient and his family. If chosen, a certified technician (Medix at Home, FDA and MOH approved) will visit the patient facility at the specific day scheduled together, in order to conveniently perform abdominal X-ray examination (required to verify Bumper flanges expulsion). A copy of the imaging will be provided to delegated sub-investigator for evaluation.

Following the X-ray examination, a delegated study member will call the patient facility to verify no technical issues occurred. The patient will be asked to report his nutritional status (malnutrition defined as a body mass index [BMI] <19 kg/m^2) and any stomal complication (wound infection, peristomal leakage, hypergranulation, pressure ulcer, any skin lesion adjacent to external bumper) – all will be investigated by the study nurse using Visit 7 safety Follow Up Form. In addition, patient will be asked regarding his postoperative morbidity, any other Adverse Events and Concomitant medications.

Alternatively, the patient will be admitted to the Gastrology Institute at Shaare Zedek Medical Center, Jerusalem an hour before the planned X-ray examination scheduled time accompanied by the study nurse. Prior to the examination he will be asked to report his nutritional status (malnutrition defined as a body mass index [BMI] <19 kg/m^2 and any stomal complication (wound infection, peristomal leakage, hypergranulation, pressure ulcer, any skin lesion adjacent to external bumper) – all will be investigated by the study nurse using Visit 7 safety Follow Up Form. In addition,

ficmedical	– Study Protocol –	Protocol No.: FM-01 Version 5.1 Page 38 of 55
Safety and Usability Evaluation of the Fidmi Low-Profile Enteral Feeding Device		CONFIDENTIAL

patient will be asked regarding his postoperative morbidity, any other Adverse Events, Concomitant medications.

The following forms will be completed:

- a) Post PEG removal imaging Form
- b) Termination visit

\*An endoscopic examination is not required but may be performed on a need base, and following the investigator discretion.

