### Un-scheduled visit:

In case particle/s from the bumper can be seen in the imaging the discharging study investigator will instruct the patient (or his care giver) to immediately refer his caring doctor in case of: vomiting, swollen belly, repeated abdominal aches and general deterioration (for demented patients). The patient must call the study nurse to schedule an un-scheduled visit only under his caring doctor discretion of: GI perforation or hemorrhage or bowel obstruction. In such case Un-scheduled visit form will be recorded. In that kind of visit the patient will be clinically managed by the study team in the Institute of Gastroenterology and Liver Diseases until. An additional X-ray imaging will be performed to illustrate and determine the localization of the retained particles. In case of colon localization the PI will consider removing those particles by colonoscopy procedure.

Version 5.1 Page 39 of 55

Safety and Usability Evaluation of the Fidmi Low-Profile **Enteral Feeding Device** 

CONFIDENTIAL

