#### Table 3 - Visit procedure chart

	Enroll and d place	evice		Follow	/ Up Per	iod	
Procedure	Screening & Enrollment	Fidmi device insertion	Sub-I visit in patient facility	Sub-I visit in patient facility	Follow up call with the patient	Fidmi device removal	X-ray and termination visit
Visits	V1	V2	V3	V4	V5	V6	V7
Time Schedule (Days)	-7	0	2	30	60	90	120
Time Window (+/- Days)	7		1	10	10	10	14
Informed consent	Х						
Demographics+ Med. history	Х						
Concomitant medications	Х	х					
Physical exam	Х	x	х	х		х	
Vital signs	Х	x	х	х		х	
Adverse event evaluation		x					
Endoscopy recording		x					
Photos of the insertion site		x	х	х		х	
PEG usability Form (physician)		х				х	
Patient Discharge form		х				х	
Safety Follow Up Form			Х	Х	Х	х	x
Tube Utilization Form (patient/care giver)			х	х	х	x	
Patient feedback Form						х	
Patient Bumper flanges							
expulsion Form							х
X-ray imaging (home/clinic)							х
Post PEG removal imaging Form							х
Termination Visit							х
Subject Visit log		Х	Х	Х	Х	х	
Un-scheduled visit Form (if needed)							

F medical	– Study Protocol –	Protocol No.: FM-01 Version 5.1 Page 40 of 55
Safety and Usability Evaluation	of the Fidmi Low-Profile	
Enteral Feeding Device		CONFIDENTIAL

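### Once the Visit 7 X-ray shows retained bumper particles, warning symptoms go to the caring doctor instead of the site, and no study contact is scheduled after that visit

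*Protocol*

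**What the plan says.** Visit 7 is headed "Follow up after 4 months +/- 10, X-ray and termination visit". It carries the only scheduled expulsion X-ray and closes the patient's participation; Table 3 has no later column. Three places govern what happens around a film with particles.

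- **Section 8.3, item 19:** if particles are visible, "a further follow visit will be scheduled only in case of symptoms related event/s, as per physician discretion".
- **Section 10.1.2, Visit 6 (Study PEG removal Form), before any film:** the patient or caregiver is told to "immediately call the site in case of: vomiting, swollen belly, repeated abdominal aches and general deterioration (for demented patients"). Where there is "suspicious of GI perforation or hemorrhage bowel obstruction the study investigator will schedule an un-scheduled visit".
- **Section 10.1.2, Un-scheduled visit, once particles are seen:** the patient or caregiver is told to "immediately refer his caring doctor in case of: vomiting, swollen belly, repeated abdominal aches and general deterioration (for demented patients"). The patient calls the study nurse to "schedule an un-scheduled visit only under his caring doctor discretion of: GI perforation or hemorrhage or bowel obstruction". The repeat X-ray and possible colonoscopic removal sit inside that visit.

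For a film taken at home, Visit 7 adds a phone call from a study member after the X-ray, which includes questions on adverse events.

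**The concern.** Passage of the bumper pieces is the new element of this removal method, and the trial is first-in-human. The patients of most interest after Visit 7 are those whose film still shows particles. For them the written route to the study team becomes longer, and the decision on whether the team hears of a symptom passes to a doctor who is not described as part of the study.

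Two things are at stake. One is delay before the study team first learns of a symptom. The other is capture: section 11.3.1 collects adverse events only up to the end of follow-up. A milder event, or one starting after Visit 7, reaches the record only if somebody reports it, and the stated rule does not ask for that report unless one of three serious diagnoses is suspected.

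**Working it through.** The plan gives no figure to reproduce. The check is a comparison of the rules, with a small calculation from the visit windows.

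**1. Symptom route before and after a positive film**

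| | Visit 6 discharge | Particles seen at Visit 7 |
|---|---|---|
| Warning symptoms | four listed | the same four |
| First contact | the site | the caring doctor |
| Who judges | study investigator | caring doctor |
| Trigger for a visit | suspected perforation, hemorrhage or obstruction | the same three events |

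The symptoms and the serious events match. The first contact and the person who judges differ. Under the Visit 6 rule the site hears of the symptom before anyone decides whether it is serious. Under the later rule it hears only after that decision, and only if the answer is yes.

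**2. Consistency with item 19**

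Item 19 allows a visit for any symptom-related event, at physician discretion. The Un-scheduled visit text limits it to three diagnoses. A patient with, say, repeated abdominal pain and no suspected perforation, bleeding or obstruction qualifies under item 19 but is not told to call.

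**3. Contact after the film**

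Planned contacts are the Visit 7 instruction to the patient or caregiver and, for home films, the Visit 7 phone call. Both belong to Visit 7. Nothing later is scheduled for a symptom-free patient.

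**4. When the film falls after removal**

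- Removal: day 90 ± 10, so day 80 to 100.
- Visit 7 by the section 10.1.2 text: day 120 ± 10, so 110 to 130. Interval: 110 − 100 = 10 to 130 − 80 = 50 days.
- Visit 7 by Table 3: day 120 ± 14, so 106 to 134. Interval: 106 − 100 = 6 to 134 − 80 = 54 days.
- Nominal: 120 − 90 = 30 days.

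These intervals describe the schedule. The protocol attaches no risk to any of them.

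**5. What a call 30 days after the film would add (this sizes the remedy, not the problem)**

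- Call day, Table 3 windows: 106 + 30 = 136 to 134 + 30 = 164; nominal 150.
- Observation after removal: 6 + 30 = 36 to 54 + 30 = 84 days; nominal 60.
- Number of calls: at most 15 if leavers are replaced and every film is positive. With the 20% + 20% loss expected in section 9.2.4 and no replacement, 15 × 0.60 = 9.

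**The case against.** The strongest reply is that this is a deliberate clinical choice. The protocol foresees a positive film and prescribes a response: instructions, an un-scheduled visit with its own form, repeat imaging and possible colonoscopy. The pieces are meant to pass naturally, and whether waiting for symptoms is adequate depends partly on preclinical results in the Investigator Brochure, which is not at hand. Section 11.2 also provides a 24-hour emergency call and guidance on un-scheduled visits. Table 3 has a bumper expulsion form at Visit 7. Section 11.3.6 arranges a visit for moderate or severe device-related events still ongoing at completion. Prior bowel obstruction and Crohn's disease are excluded.

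Most of this stands, and it rules out several stronger readings that a reader might infer:

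- *That patients hold two conflicting instructions.* The instructions are sequential. The second is given after the film and would naturally replace the first.
- *That there is no contact at all after a positive film.* The Visit 7 instruction and the home-film call are planned contacts.
- *That the symptom lists are deficient because they omit painful defecation, an anticipated post-removal complication.* The lists are urgent warning signs, and item 19's discretion could cover that complaint.
- *That the caring doctor will know nothing of the device.* Sections 13.3 and 13.5.1 provide for informing the family physician. The text does not say whether this is the same person, so neither conclusion is secure.

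The reply leaves two points unanswered. It does not explain why the route to the site should lengthen once fragments are known to be present, or why the visit rule is narrower than item 19. Nor do the safeguards fill the capture gap: section 11.3.6 does not reach events that begin after completion, and the 24-hour call depends on the patient choosing to use it despite a doctor-first instruction.

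**Conclusion.** The point holds as a defect in a stated rule and should be corrected. Followed exactly, the protocol gives patients with a positive film a less direct route to the study team than they had at Visit 6, and a narrower trigger than item 19. It also schedules nothing for them after Visit 7, so milder or late-onset fragment-related events may go unrecorded.

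The size is modest. It concerns at most about 15 patients, and only those with a positive film; the protocol gives no retention rate, so the actual number cannot be stated. Suspected serious events do return to the study team. It would be tempting to infer that retained fragments are shown to be dangerous, or that the safety endpoints are biased. The document supports neither. The conclusion assumes that the Un-scheduled visit text is applied as written and that the Investigator Brochure contains no overriding instruction.

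**What to change.** **Main change, section 10.1.2, Un-scheduled visit.** Have patients with a positive film, or their caregivers, call the site directly for the listed symptoms, as at Visit 6. The study investigator then decides on an un-scheduled visit for any symptom-related event, matching item 19. State that urgent care from any doctor must not wait for this call.

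**Cheap addition.** For patients with a positive film only, add one safety phone call on the existing Safety Follow Up Form about 30 days after the film. The interval is a judgement; nothing in the protocol fixes it. List events after Visit 7 separately, so that the safety endpoints counted to study completion cover the same follow-up in every patient. Item 19, Visit 7 and Table 3 need a matching line. The duration statements in the Synopsis and section 7.3 need a sentence too. If their 120 ± 14 days is counted from insertion, it ends at day 134, before the earliest call at day 136. The Synopsis reads "Per Patient: between 120 days±14 days, depending on the interval between pre-operative visit (inclusion) and day of operation", so day 134 is one reading of the limit rather than a firm one.

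**Cost.** At most about 15 calls, with those cases closing about 30 days later; an amendment with IRB review, and MOH approval if it is judged medically significant (section 13.4.2); and possible re-consent of patients already enrolled. No new form or required imaging is needed. The call does not confirm expulsion. Further imaging and treatment stay at the investigator's discretion.

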#### 8.4 SAMPLE SIZE JUSTIFICATION

15 adult patients, males or females, scheduled for PEG (Newly PEG insertion and PEG replacement involving endoscopy procedure). There will be minimum of 10 Newly PEG inserted patients enrolled to the study from the overall sample size.

Due to the small sample size and study early stage, no formal sample size calculation was done for this study.

#### 9 SELECTION AND WITHDRAWAL OF SUBJECTS

#### 9.1 STUDY POPULATION AND JUSTIFICATION

Adult patients, males or females suffering from dysphagia who are scheduled for PEG (Newly PEG insertion and PEG replacement involving endoscopy procedure) with protocol local anesthetic. There will be minimum of 10 Newly PEG inserted patients enrolled to the study from the overall sample size.

The enrollment of patients to be studied in the clinical trial will respect a gender criterion in order to involve a similar number of male and female patients in the study and highlight any specific differences observed that might refer to biological characteristics and social/cultural factors.

#### 9.2 ELIGIBILITY CRITERIA

#### 9.2.1 Inclusion Criteria

- 1. Male or female patient 18 up to 90 years.
- 2. Consecutive adult patients suffering from oropharyngeal dysphagia impairing or anticipated to impair the patients' nutritional status with need for enteral feeding (PEG).
- 3. Ability to give informed consent for the study by patient or legal guardian.

ficmedical	– Study Protocol –	Protocol No.: FM-01 Version 5.1 Page 26 of 55
Safety and Usability Evaluation Enteral Feeding Device	of the Fidmi Low-Profile	CONFIDENTIAL

4. Willingness to undergo 4 follow up visits 1, 3 and 4 months following PEG insertion/replacement, as well as unscheduled sick visits.

#### 9.2.2 Exclusion Criteria

- Pregnancy (all women of child-bearing age would be questioned and told 1. by the consenting physician regarding that criteria).
- 2. All current practice PEG contraindication
- 3. Acute gastrointestinal bleeding
- 4. Extreme obesity patients (BMI>40)
- 5. Emergency endoscopy
- 6. Infectious disease local or systemic (e.g.- sepsis, pancreatitis)
- 7. Known esophageal pathology (e.g.- stenosis, eosinophilic esophagitis, varices, achalasia, reflux)
- 8. In case of PEG replacement: lack of a well healed gastrostomy or Infection around the insertion site.
- 9. Known gastric pathology that may prevent safe device insertion, feeding, removal and Bumper flanges expulsion according to the investigator discretion.
- 10. Any history of bowel obstruction, pseudo-obstruction.
- 11. Crohn's disease
- 12. Severe GERD, recurrent vomiting
- 13. Inability to tolerate sedated upper endoscopy due to cardio-pulmonary instability or other contraindication to endoscopy
- 14. Current enrollment in an investigational drug or device study or participation in such a study within 30 days of entry into this study.

#### Withdrawal 9.2.3 Reasons for or Termination (Early **Discontinuation**):

Patients will be removed from study when any of the criteria listed below applies. The reason/s for study removal and the date in which the patient was removed will be documented in the Case Report Form (CRF):

- 9.2.3.1 Patients not complying with the protocol requirements.
- 9.2.3.2 AE resulting in discontinuation of the study.
- 9.2.3.3 Patient decides to withdraw from the study.
- 9.2.3.4 IRB request to discontinue the study.

fic medical	– Study Protocol –	Protocol No.: FM-01 Version 5.1 Page 27 of 55
Safety and Usability Evaluation of the Fidmi Low-Profile Enteral Feeding Device		CONFIDENTIAL

- 9.2.3.5 Lack of adherence of stomach to abdominal wall.
- 9.2.3.6 Inability to complete Fidmi device gastrostomy placement

#### 9.2.4 Handling of Participant Withdrawals or termination

The participation in the study, as in any clinical study, is voluntary and participants are allowed to withdraw from the study at any time.

Participants who leave the study prematurely will be replaced. A patient discontinuing the study before Fidmi PEG placement can be replaced, at the discretion of the investigator, by another consenting patient. The discontinuing patient will be followed for safety.

We anticipate from previous reports (9) that about 20% will not complete the 4 months study due to death and addition of 20% will withdraw from the study due the above listed reasons.

Each case of premature withdrawal will be properly recorded. As deemed necessary.

### 9.3 9.3 SUBJECT ENROLLMENT 9.3.1 SCREENING

The study will be conducted both in the Gastrology Institute at Shaare Zedek Medical Center, Jerusalem, Israel and in the Gastrology Institute at Hadassah Medical Center, Jerusalem, Israel. Prior to any study-related screening procedure, delegated study team members (investigators and nurses) will approach potentially eligible adults subjects suffering from oropharyngeal dysphagia impairing or anticipated to impair the patients' nutritional status, who are waiting to be scheduled for PEG insertion or replacement, involving endoscopy procedure. Those who may be eligible will be offered the choice of undergoing screening to potentially enroll in the study or receiving free treatment for their current illness without participating in the study. Subjects who do not meet inclusion criteria or who are for any other reason determined to be too ill for inclusion in the study, or who decline to participate in the study, will be considered and recorded as "screen failure" and receive standard and appropriate treatment.

ficmedical	– Study Protocol –	Protocol No.: FM-01 Version 5.1 Page 28 of 55
Safety and Usability Evaluation of the Fidmi Low-Profile Enteral Feeding Device		CONFIDENTIAL

#### 9.3.2 CONSENTING

Consenting will be performed at the Gastrology Institute at Shaare Zedek Medical Center. In case of 'special population consenting' (demented patients) a designated consenting form (3A) as deemed by the Israeli MOH (HANOHAL) will be signed by the patient guardian and a copy of the signed Apotropos authorization documents would be collected and documented in the patient binder . Any use of study samples that is outside the scope of the objectives of this protocol will be submitted for prior review and approval by the appropriate IRBs. The informed consent document will be signed and dated for screening and enrollment and each subject consenting will be documented in the study doctor's letter at the time of enrollment. The clinician will ask the patient about his plans and his willingness to attend all scheduled and unscheduled follow-up visits.

#### 9.4 SUBJECT IDENTIFICATION

Patients will be identified by a serial number and will be numbered according to the site number (first digit) and their recruitment (2nd and 3rd digits): e.g. 101, 203 etc.

#### 9.5 SCREENING FAILURE

Patients who have not fulfilled all the inclusion criteria, or have fulfilled one of the exclusion criteria will not be included in this study. Patient who have screen failure will be replaced.

